	-56 to -21	-49 to -14									
Study Days	Clinic Visit 1	Clinic Visit 2	1	14 ± 3	28 ± 3	56 ± 3	84 ± 3	112 ± 3	140 ± 3	168 ± 3	196 ± 7
Clinic Visits			Clinic Visit 3	n/a	Clinic Visit 4	Clinic Visit 5	Clinic Visit 6	Clinic Visit 7	Clinic Visit 8	Clinic Visit 9	Clinic Visit 10
Phone Call				X							
Patient/Caregiver/ Clinician Global Impression of Symptoms			X		X		X			X	
Clinician assessment of xanthoma			X				X			X	
Pregnancy test m	X serum	X urine	X urine		X urine	X urine	X urine	X urine	X urine	X urine	X urine
Study drug dispensed n			X		X	X	X	X	X	X	
Adverse events o	All Adverse Events										
FSV Deficiency Questionnaire	X	X	X	X	X	X	X	X	X	X	X
Study drug compliance				X	X	X	X	X	X	X	X
eDiary compliance i		X	X	X	X	X	X	X	X	X	X
Exit Interview										X	

AFP: alpha-fetoprotein; eCRF: electronic case report form; eDiary: electronic diary; EOT: end of treatment; FSV: fat soluble vitamin; ICF: informed consent form; INR: international normalized ratio; p-C4: plasma 7α hydroxy 4-cholesten-3-one; PedsQL: Pediatric Quality of Life Inventory; PK: Pharmacokinetic; QoL: quality of life; SAE: serious adverse event.

a All assessments will be performed before dosing unless otherwise noted.

b The two screening visits must be separated by at least 7 days, and Screening Visit 2 must occur at least 14 days prior to Study Day 1.

c An EOT visit must be performed as soon as possible if study drug is prematurely discontinued. The EOT visit requires the same assessments as the Week 24 visit.

d The Safety Follow-up visit is required 28 days (±7) following the Week 24/EOT visit or the date of last dose for patients who prematurely discontinued study treatment. See Section 7.1.3 and Section 7.1.4 for when a Safety Follow-up visit is not required.

- e The ICF (and assent) must be signed before any study procedures are performed.
- f Past (within 28 days prior to Screening Visit 1) and current medication will be documented in the eCRF.
- g A full physical exam including skin exam will occur at Screening Visit 1 and Day 1. At all other clinic visits a skin exam and symptom-based physical exam will occur. Findings from the symptom-based physical exam will be documented as adverse events if appropriate.
- h Includes blood pressure, pulse, respiratory rate, temperature, height (or length depending on age), and body weight.

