### 10.1 Adverse Events

#### 10.1.1 Safety Reporting Period

Each patient must be carefully monitored for the development of AEs during the safety reporting period.

The safety reporting period for adverse events is from the first dose of study drug through the last planned study visit or 28 calendar days after the last dose of the study drug, whichever occurs later. The safety reporting period for serious adverse events is from signing of the informed consent form through the last planned study visit or 28 calendar days after the last dose of the study drug, whichever occurs later.

An SAE that occurs following the safety reporting period and which is assessed by the investigator as related to study medication should also be reported.

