#### **10.1.3 Recording of Adverse Events**

Patients must be carefully monitored for the development of any AEs during the safety reporting period.

All observed AEs and any AEs that are spontaneously reported by the patient/caregiver will be recorded by the investigator. For all AEs, the severity, seriousness, and causality to study drug for each AE as outlined in [Section 10.1.2](#) will be assessed and recorded in the eCRF.

Any AE assessed as serious must be reported within 24 hours of site awareness.

Any SAEs or AEs that lead to permanent discontinuation of study drug that are unresolved at the time of the last study visit will be followed up by the investigator until resolution or stabilization. Following the last study visit, the Sponsor will provide forms for reporting additional information for any patient with ongoing SAEs or AEs that led to permanent discontinuation of study drug. Albireo retains the right to request additional information for any patient with ongoing AE(s) or SAE(s) at the end of the study.

Treatment-emergent AEs are defined as any AE that occurs after first dose of study drug. All SAEs that occur in the Screening Period, i.e. after enrollment and prior to first dose of study drug, will be collected as non-treatment emergent SAEs.

If there is a clinically significant deterioration of a laboratory value/vital sign or other routine study assessment that is associated with a diagnosis, the clinical diagnosis will be reported

as an AE and the associated signs and symptoms will be considered additional information unless the sign or symptom is more severe than expected given the diagnosis. For example, in a patient diagnosed with hepatitis during the safety reporting period, hepatitis would be considered the AE. Signs and symptoms of abdominal pain, vomiting, and elevated ALT and AST would not be reported separately unless, in the opinion of the investigator, one of these signs or symptoms is more severe than expected and therefore a separate AE assessment is indicated.

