1.1 Study Design

This is a phase 3, double-blind, randomized, placebo-controlled study to investigate the efficacy and safety of 120 µg/kg/day odevixibat compared to placebo in patients with Alagille syndrome (ALGS).

Figure 1 – Study Design

Odevixibat = once daily treatment with 120 µg/kg/day odevixibat

The study includes a screening period of up to 56 days, followed by a 24-week treatment period, and a Safety Follow-up Period. Eligible patients will be randomized 2:1 to receive odevixibat 120 µg/kg/day or placebo. An Interactive Web Response System (IWRS) will be used to assign patients to treatment. The randomization codes were computer generated by a qualified randomization vendor. An experimental cohort of approximately 45 patients <18 years of age at randomization with a genetically confirmed diagnosis of ALGS will be enrolled. Patients <18 years of age will be randomized according to an age stratification factor, i.e., <10, and 10 to <18 years of age. The protocol included an additional exploratory cohort of patients ≥18 years of age with a genetically confirmed diagnosis of ALGS, not to exceed 18 patients in total, who were also to be randomized 2:1 favoring active treatment. A separate randomization scheme was provided for this cohort. There were no subjects enrolled in this cohort at the time enrollment completed for the study.

Patients who complete the Week 24/EOT visit in this study will be invited to participate in an open-label extension study in which all patients will receive active treatment. Patients who enroll in the open-label extension study will not participate in the Safety Follow-up Period.

There will be two treatment groups in this study, odevixibat 120 µg/kg/day and placebo. Odevixibat and placebo will be supplied as capsules for oral administration. The number of capsules provided to the patient will be based on body weight at randomization (Study Day 1) and can be adjusted depending on the patient’s weight (Protocol Table 2) at each study visit.

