4.8.1 Adverse Events

General common rules for summarizing adverse events

All AEs will be classified by SOC and PT using the MedDRA version 25.0.

AEs will be classified as TEAEs, defined as follows: An AE (classified by preferred term) that occurs during the Treatment Period will be considered a TEAE if it has a start date on or after the first dose date of study drug, or it has a start date before the date of the first dose date of study drug but worsened in severity on or after the date of the first dose date of study drug.

AEs with missing start dates, but with stop dates either overlapping with the treatment period or missing, will be considered TEAEs. A TEAE with missing drug-relationship will be considered as related. A TEAE with missing severity will be considered as CTCAE grade 3 (severe). Details for imputing missing or partial start dates of adverse events are described in [Appendix 5](#). AEs with the same AE reference number that is collected on AE page of eCRF are counted as one AE only.

Adverse events of interest (AEIs)

Adverse events of interest (AEIs) will be selected for analyses as indicated in [Table 6 - Selections for AEIs](#).

Table 6 – Selections for AEIs

AEIs	Selection
Liver Decompensation	
a. The following TEAEs will be included:
 
PT = International normalised ratio increased and checkbox that event is refractory to vitamin supplementation is checked and at least 1 INR value (within 2 weeks [+/-] of the AE started date) is >1.5
 
PT = Vitamin K increased and checkbox that event is refractory to vitamin supplementation is checked and at least 1 INR value (within 2 weeks [+/-] of the AE started date and checkbox) is >1.5
 
PT = Hepatic failure, Acute on chronic liver failure, or Subacute hepatic failure
 
b. The following TEAEs occurring as separate events or in the presence of (i.e. ongoing medical history or AE) PT of portal hypertension and/or PT of hepatic cirrhosis were included:
 
PT = Ascites
 
PT = Hepatorenal syndrome
 
PT = Portopulmonary hypertension
 
PT = Oesophageal varices haemorrhage
 
PT = Gastric varices haemorrhage
 
PT = Intestinal varices haemorrhage
 
PT = Hepatic encephalopathy

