Summary tables for number of patients with any TEAEs by SOC and PT by severity (grade 1 to grade 5) and by causality (related [possibly, probably, and definitely] vs unrelated [unlikely and unrelated]), will also be provided. AEs with the worst severity will be used in the by-severity summaries. Similarly, AEs with the worst causality (most related to treatment) will be used in the by-causality summaries. If severity or causality is missing, data will be imputed as grade 3 or related, respectively.

When a patient has the same adverse event, based on preferred terminology, reported multiple times during the study, the patient will only be counted once at the preferred terminology level in adverse event frequency tables. Where a patient has multiple adverse events within the same SOC during the study, the patient will only be counted once at the SOC level in adverse event frequency tables. In the AE summaries, AEs will be sorted by alphabetically for SOC and PT.

In addition to the frequency summary of TEAE tables, the exposure adjusted incidence rate (EAIR) (per 100 patient years at risk) with the 95% confidence interval, based on Poisson distribution, will also be provided for each of the following AE tables:

- TEAEs by SOC and PT
- Liver-related TEAEs by SOC and PT
- Liver Decompensation TEAEs (as defined in [Table 6 - Selections for AEs, for TEAEs listed in b in the presence of \(i.e. ongoing medical history or AE\) PT of portal hypertension and/or PT of hepatic cirrhosis](#)) by SOC and PT
- FSV Deficiency refractory to clinically recommended vitamin supplementation TEAEs by SOC and PT
- Possible Sequelae of FSV Deficiency TEAEs by SOC and PT
- Clinically Significant Diarrhea TEAEs by SOC and PT

The EAIR (per 100 patient years at risk) will be calculated as follows:

$$\text{Number of subjects with event} / \text{Total cumulative time at risk (years)} \times 100$$

where total cumulative time at risk is the sum of individual time at risk. The time at risk for a subject with the event of interest will be calculated (in years) as:

$$(\text{first event date} - \text{date of first dose} + 1) / 365.25$$

The time at risk for a subject without the event of interest is calculated as:

$$(\text{last participation date} - \text{date of first dose} + 1) / 365.25$$

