5.2 Appendix 2 Derived Variables

The table below provides the list of derived variables for demographic and baseline characteristics, various duration derivations, drug compliance, baseline derivations and other important protocol derivations applicable for this study.

Table 9 – Derivation rules for the derived variable

Variables	Formula
Demographic and Baseline characteristics	
Age (in years)	For patients not from site CCI : Age is calculated based on date of birth and date of randomization. It will be derived by SAS YRDIF function: yrdif (Date of birth, Date of Randomization, "ACT/ACT") For patients from site CCI : Only year of birth was collected, and January 1 was imputed in the eDC system. For analysis purpose, age is calculated based on collected age months and age years on the CRF.
Derivation of Duration	
Study day at any visit	Date of interest – Date of first dose of study drug. One day is added if this difference is ≥ 0
Extent of Exposure	
Duration of treatment exposure (days)	Date of last study drug intake – Date of first study drug intake + 1
Average Daily dose (ug/kg/day)	Sum of (number of capsules taken per day * dose strength of the capsules per weight category * dose duration under this dose amount/weight) / (Date of last study drug intake – Date of first study drug intake + 1)
Overall Study Drug Compliance	
Compliance	$100 \times \text{sum of (number of capsules actually taken)} / \text{sum of (number of capsules planned to be taken per day * dose duration under this planned dose amount)}$
Last participant date	Last contact date or date of death which occurred first
Derivation for Efficacy Parameters	
Baseline (general)	The baseline value of a parameter is defined as the last assessment of that parameter prior to the first intake of study treatment, except as indicated below
Baseline for serum bile acid	The baseline will be calculated as the average of the last 2 values prior to the first dose (central laboratory results will be used over local laboratory results). If only one non-missing value is available, it will be used as baseline.
Average serum bile acid of Week 20 and Week 24	The average of values that identified from analysis window at Week 20 and Week 24.
Daily score for ObsRO scratching (or PRO itching) severity	The daily score is calculated by averaging the PM score and the next day AM score. The daily score is calculated if at least the PM score or the next day AM score is collected.

Variables	Formula

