Average Month 4 to 6 and change from baseline	Average of all available monthly scores through Month 4 to 6. Change from baseline through Month 4 to 6 is calculated by subtracting the baseline score from the average of monthly scores through Month 4 to 6.
Baseline and monthly score for sleep parameters (such as difficulty of falling asleep and staying asleep, tiredness, and the number of awakening)	For patient- and observer- reported outcome scores of sleep parameters, the same approach above will be used as for scratching (or itching) severity score by AM and PM respectively since there is just 1 rating per day.
PRO and ObsRO Assessment Scores for psychometric analyses	Please refer to psychometric analysis plan
Derivation for Safety Parameters	
AE duration (days)	AE end date – AE start date +1
TEAE	An AE (classified by preferred term) that occurs during the Treatment Period will be considered a TEAE if it has a start date on or after the first dose date of study drug, or it has a start date before the date of the first dose date of study drug, but worsened in severity on or after the date of the first dose date of study drug

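### The SAP limits a TEAE to the Treatment Period, against the protocol's definition, while time at risk and Kaplan-Meier censoring run on to last contact

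*SAP*

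**What the plan says.** **Numerator.** SAP section 4.8.1 opens its definition with "An AE (classified by preferred term) that occurs during the Treatment Period will be considered a TEAE". The sentence goes on to require onset, or worsening in severity, on or after first dose. SAP Table 9 (Appendix 2) repeats the restriction, with the same conditions. SAP section 1.1 describes screening "followed by a 24-week treatment period, and a Safety Follow-up Period", so the two are successive periods.

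**Protocol.** Section 10.1.3 has a wider definition: "Treatment-emergent AEs are defined as any AE that occurs after first dose of study drug". Section 10.1.1 collects AEs from first dose "through the last planned study visit or 28 calendar days after the last dose of the study drug, whichever occurs later".

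**Denominator.** For the EAIR, SAP section 4.8.1 says: "The time at risk for a subject without the event of interest is calculated as" the days from first dose to the last participation date, in years. Table 9 lists what is evidently the same date as "Last contact date or date of death which occurred first". Patients without an event are censored at last contact in the Kaplan-Meier curves.

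**Missing dates.** SAP Appendix 5 makes an AE with a missing start year a TEAE unless it ended before first dose. It sets no upper limit.

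**Declared changes.** SAP Table 8 lists changes to the protocol-planned analyses. The TEAE definition is not among them.

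**The concern.** The primary safety analysis is TEAE incidence (SAP section 4.8). The AE overview and the tables by SOC and preferred term, severity, causality and event of interest are all TEAE tables. No table of post-treatment AEs is planned. A liver event that starts during the Safety Follow-up would be collected and listed but would not appear in any planned TEAE incidence table.

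The rates have a second problem. If follow-up events cannot enter the numerator, follow-up days should not enter the denominator. As written they do, which lowers the EAIR. With about 45 patients, one uncounted event of interest can change how a table reads.

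**Working it through.** The documents give no figure on this point, so there is none to reproduce. The check compares the rules and then sizes the mismatch.

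**1. Rules side by side**

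| Rule | Upper limit |
|---|---|
| TEAE, SAP 4.8.1 and Table 9 | Treatment Period |
| TEAE, protocol 10.1.3 | none stated |
| AE collection, protocol 10.1.1 | later of last planned visit and 28 days after last dose |
| AE with missing start year, SAP Appendix 5 | none |
| EAIR time at risk, no event | last contact or death |
| Kaplan-Meier censoring | last contact |

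Only the TEAE rule stops at the Treatment Period. A follow-up AE with a known start date is excluded, but the same AE with a missing start year is counted.

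**2. Inputs for size**

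- Treatment period: 24 weeks = 168 days (SAP section 1.1).
- Follow-up: "The Safety Follow-up visit is required 28 days (±7) following the Week 24/EOT visit" (protocol Table 1), so nominally 28 days, range 21 to 35.
- Patients who enter the extension have no Safety Follow-up Period (SAP section 1.1).
- Assumptions: constant event rate on and off drug, events rare enough that few patients stop the clock early, all patients complete 168 days, and a share f of the arm does not roll over.

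**3. One completer who does not roll over**

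Ratio of literal EAIR to true rate = 168/(168 + 28) = 168/196 = 0.857. The uncountable share is 28/196 = 14.3%. With 21 days it is 21/189 = 11.1%, and with 35 days 35/203 = 17.2%.

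**4. A whole arm**

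Ratio = 168/(168 + 28f).

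| f (assumed) | Denominator | Ratio | Understatement |
|---|---|---|---|
| 10% | 170.8 | 0.984 | 1.6% |
| 20% | 173.6 | 0.968 | 3.2% |
| 30% | 176.4 | 0.952 | 4.8% |
| 50% | 182.0 | 0.923 | 7.7% |
| 100% | 196.0 | 0.857 | 14.3% |

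**5. Illustration that separates the two effects**

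Take a hypothetical arm of 30 in which 24 patients roll over and 6 have 28 days of follow-up. Three rollover patients have an event on day 84, and one follow-up patient has an event only on day 182.

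- SAP as written: 3×84 + 21×168 + 6×196 = 4,956 days; 3 events; 3/(4,956/365.25)×100 = 22.1 per 100 patient-years.
- Numerator and denominator both cut at end of treatment: 3×84 + 21×168 + 6×168 = 4,788 days; 3 events; 22.9.
- Protocol definition: 3×84 + 21×168 + 5×196 + 182 = 4,942 days; 4 events; 29.6.

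The step from 22.1 to 22.9 is the denominator mismatch. The step to 29.6 is the uncounted event. That event is invented, so 29.6 shows the mechanism and is not an estimate.

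**6. Kaplan-Meier**

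Later censoring does not change risk sets before Week 24. The effect is a tail after Week 24 that must be flat, because no TEAE can occur there.

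**The case against.** The strongest reply is that the phrase has no effect. The SAP gives the Treatment Period no end date. Both conditions that follow it refer only to first dose, Appendix 5 has no post-treatment category, and time at risk and censoring run to last contact. On this view the authors meant the protocol's window, and Table 8 had nothing to declare. That may well be the intent, and the documents do not show a deliberate narrowing. But the restriction is written twice, and the missing-start-date rule in section 4.8.1 also uses the treatment period as a window. A programmer who follows the text would exclude follow-up events. The reply shows that the SAP contradicts itself, which is a reason to correct it.

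The reply on size largely stands. The mismatch touches six EAIR tables and Kaplan-Meier curves that are optional. The clock stops at first event, so common events are diluted less. No inferential safety analysis is planned.

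A reader might infer three stronger points that the documents do not support:

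- *Follow-up events vanish from all safety output.* Protocol section 11.2.2.8 requires listings of all safety parameters. Special situations are summarized without a TEAE limit, and SAP section 4.8 names all-cause mortality.
- *A patient who stops on day 56 and is followed to day 168 has 112/168 = 67% uncountable time.* This needs the Treatment Period to mean time on drug. SAP section 1.1 makes it 24 weeks, and protocol section 7.1.4 speaks of stopping drug within it.
- *Follow-up holds mainly patients with poor tolerability, so one arm is favored.* This is conjecture. Under protocol section 7.1.4, early stoppers who keep attending scheduled visits need no Safety Follow-up visit.

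**Conclusion.** The point holds as a conflict in the written rules. The SAP's TEAE window is narrower than the protocol's, disagrees with the SAP's own Appendix 5, is not declared in Table 8, and does not match the SAP's time at risk. Taken literally, it removes events with onset in the Safety Follow-up from every planned TEAE table.

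The effect on rates is modest: 14% for a single completer with 28 days of follow-up, and about 2% to 5% for an arm at an assumed 10% to 30% non-rollover share. Those figures rest on a constant rate on and off drug, rare events and full completion. The number of follow-up events that would go uncounted cannot be estimated from the documents. A between-arm bias is not shown; it would arise only if follow-up time or follow-up events differed by arm.

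**What to change.** In SAP section 4.8.1 and Table 9, replace the Treatment Period condition with onset or worsening from first dose to the end of the safety reporting period in protocol section 10.1.1. For patients who roll over, end the window when participation in this study is complete under protocol section 7.2.5. End EAIR time at risk and Kaplan-Meier censoring for TEAEs on that same date, and give the missing-date rules in section 4.8.1 and Appendix 5 the same upper limit.

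If the narrower window is intended, declare it in Table 8, give the Treatment Period an explicit end date, cut time at risk and censoring to match, and add a table of post-treatment AEs.

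The cost is SAP wording and a few derivation rules, settled before unblinding. No new data are needed. The only downside is that some AE counts may rise slightly.
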